4.5.2 Acceptable methods of contraception

Women of childbearing potential [see definition in Section 4.5.1] must use one of the following methods of birth control from Screening up to at least 30 days after study treatment administration:

1. Diaphragm / female condom / cervical cap / partner's use of a condom.
2. Intra-uterine devices.
3. Oral or injectable contraceptive agents, implants, or transdermal contraceptive hormone patches. If a hormonal contraceptive is chosen, it must be taken for at least 1 month prior to randomization.
4. Sterilization method (tubal ligation / occlusion, or partner's vasectomy).
5. True abstinence from intercourse with a male partner only when this is in line with the preferred lifestyle of the subject.

Rhythm methods are not considered as acceptable methods of contraception for this study.

The methods of birth control used (including non-pharmacological methods) must be recorded in the CRF.

5 TREATMENTS

5.1 Study treatment

5.1.1 Investigational treatment and matching placebo: Description and rationale

Study treatment for s.c. administration will be available as sealed glass vials in 1 strength: 20 mg. The vials contain 22 mg of lyophilized ACT-246475A (hydrochloride salt of

ACT-246475) or matching placebo to be reconstituted with 1 mL of water for injection. The s.c. formulation contains mannitol as an inactive ingredient.

Study treatment will be given as a single dose, administered s.c. at site by qualified personnel (e.g., nurse, physician).

ACT-246475 at 2 different doses (8 and 16 mg) and placebo will be administered during this study. The ACT-246475 doses have been selected based on data from the SAD AC-076-102 study and on modeling to meet the following criteria:

- The low dose (8 mg) is the minimal dose achieving at least 85% IPA for 3 h which corresponds to a time period during which complete suppression of platelet reactivity is needed before specific in-hospital management of ACS [Montalescot 2014].
- The high dose (16 mg) provides IPA of at least 85% in no more than 5% of the subjects at 8 h. This corresponds to the maximal time accepted to limit interference with invasive and/or pharmacological standard of care of AMI.

These 2 doses are considered distinct enough to allow further modeling of the optimal phase 3 dose based on study data.

Note: onset of action of ACT-246475 is not dose-dependent and therefore did not account for dose selection.

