4.3 Inclusion criteria

For inclusion in the study, all of the following inclusion criteria must be fulfilled. It is not permitted to waive any of the criteria for any subject:

1. Signed informed consent prior to any study-mandated procedure.
2. Male and female subjects aged from 18–85 years, inclusive.
3. For women of childbearing potential: Negative urine pregnancy test at Visit 1 and at Visit 2 before randomization.
4. Stable CAD defined by the presence of any of the following conditions:
 - a. History of CAD with coronary artery stenosis on coronary angiogram $\geq 50\%$.
 - b. Previously documented MI occurring more than 3 months prior to randomization.
5. Antiplatelet background therapy stable for at least 1 month prior to randomization.
6. Body weight ≥ 40.0 kg (88.2 lbs).

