5.1.8 Study treatment dose adjustments and interruptions

Study treatment dose adjustments are not permitted.

Study treatment interruptions are not applicable for this single-dose study.

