3.3 Other objectives

The other objectives of this study, following a single s.c. administration of ACT-246475, are:

- To assess the pharmacokinetics (PK) of ACT-246475.
- To assess the impact of the injection site location (thigh vs abdomen) on the PK and pharmacodynamics (PD) of ACT-246475.
- To investigate the impact of concomitant drug use, age, sex, and other covariates on the PK and PD of ACT-246475.
- To investigate the safety and tolerability of ACT-246475.

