The estimated proportion of responders and the corresponding 95% CI will be provided overall and by injection site, for each treatment arm.

A logistic regression analysis of the PD response will be performed to test for treatment effect (8 mg, 16 mg, and placebo) using the following covariates: injection site (abdomen, thigh), PRU level at randomization (stratification levels), age (continuous), sex (male, female), and assessment time (minutes) as continuous.

A longitudinal analysis of the treatment effect, from start of treatment up to 8 hours after injection, on platelet reactivity as measured by VerifyNow®, i.e., PRU value, will be performed using a mixed model with PRU as the dependent variable, subject as a random factor, and treatment (8 mg, 16 mg, and placebo), injection site (abdomen, thigh), PRU level at randomization (stratification levels), age (continuous), sex (male, female), and assessment time (minutes) as fixed factors. The model will also include

(treatment \times injection site) as an interaction term to assess consistency of treatment effect across injection sites.

IPA as measured by VerifyNow® will also be summarized at each time point as a continuous parameter.

The evolution of PRU values over time will be described using box-and-whisker plots, visualizing mean, median, interquartile ranges, SD, and outliers.

Assuming a treatment \times injection site interaction, summary and graphical analyses described above will be repeated by site injection sub-group.

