6.9 Analysis of pharmacokinetic variables

The PK variables will be summarized and listed using the PK set.

The plasma PK parameters of ACT-246475 will be derived by non-compartmental analysis of the plasma concentration-time profiles. PK endpoints include: maximum observed plasma concentration (C_{max}), time to reach C_{max} (t_{max}), and the area under the plasma concentration-time curve from time zero to 24 h time point (AUC_{0-24h} ; study drug administration to 24 h time point post administration).

Log-transformed value of C_{max} and AUC_{0-24h} , will be used in the analysis.

The PK parameters (linear and log-transformed ones) will be summarized by dose group using descriptive statistics, i.e., arithmetic mean, SD, geometric mean, minimum, median, maximum, standard error, and 2-sided 95% CI of the means and coefficient of variation in %. Graphical representation of PK results over time (scheduled time point) will be provided using box-whisker plots. For t_{max} , the geometric mean and its 95% CI will not be calculated.

PK variables summary will be provided by dose, injection site, PRU category used for stratification, and by gender.

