7.6.2 Body weight, and other vital sign analyses

Body weight values and assessment date will be listed.

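### Doses are fixed in mg and entry starts at 40 kg, but SAP 6.9 has no body-size analysis of PK and the PD models carry sex without weight, so any weight effect would be mixed with sex.

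*Protocol*

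**What the plan says.** Protocol 5.1.1 sets two doses in mg: "ACT-246475 at 2 different doses (8 and 16 mg) and placebo will be administered during this study". Protocol 5.1.8 adds: "Study treatment dose adjustments are not permitted". The only weight limit in Protocol 4.3 is a lower one, "Body weight ≥ 40.0 kg (88.2 lbs").

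Among the other objectives, SAP 3.3 (matching Protocol 2.2) lists: "To investigate the impact of concomitant drug use, age, sex, and other covariates on the PK and PD of ACT-246475".

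The planned analyses use body size as follows.

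- **PK (SAP 6.9).** Descriptive statistics only: "PK variables summary will be provided by dose, injection site, PRU category used for stratification, and by gender". There is no regression model and no weight or BMI split.
- **PD response, logistic model (SAP 6.8.1.2).** The model is fitted "using the following covariates: injection site (abdomen, thigh), PRU level at randomization (stratification levels), age (continuous), sex (male, female"), plus assessment time.
- **PRU, longitudinal mixed model (SAP 6.8.1.2).** Treatment, injection site and their interaction, with "PRU level at randomization (stratification levels), age (continuous), sex (male, female), and assessment time (minutes) as fixed factors".
- **8 h aggregation status (SAP 6.8.2.2).** Treatment, injection site and their interaction, PRU level, age and sex.
- **BMI.** Three classes form a subgroup for the primary PD endpoint (SAP 6.8.1.4). SAP 6.8.2.4 applies the same subgroups descriptively to the other PD endpoints; its cross-reference points to itself, but 6.8.1.4 is evidently meant.
- **Body weight.** Tabulated as a demographic, overall and by gender (SAP 5.4.1). In the safety section, "Body weight values and assessment date will be listed".

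**The concern.** Under a fixed dose, a lighter subject receives more drug per kilogram. If women in the trial are lighter on average than men, a by-gender PK table and a sex coefficient in a PD model without weight estimate the effect of sex and weight together. A reader could take the result for an effect of sex when weight is the cause.

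This matters here for two reasons. The three earlier human studies in Protocol 1.3.2 enrolled healthy men, so among the listed studies this trial gives the first PK and PD data in women. Protocol 5.1.1 also says that the data will feed modelling of the phase 3 dose. A sex difference and a weight difference would lead that work in different directions.

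A weight effect on exposure could also reach the PD endpoints. Protocol 1.3.2.3 reports dose-proportional exposure and a dose-dependent duration of effect. The primary response and the 8 h status both depend on duration.

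**Working it through.** **1. The plan's own figures.** The plan states no weight-related figure. Its sample size reproduces and does not involve weight.
- Versus placebo, log-odds-ratio form: (2.241 + 1.282)² × [1/(0.5×0.5) + 1/(0.75×0.25)] / (ln 3)² = 95.98, so 96 per arm.
- Versus 70%: [(2.241×√0.21 + 1.282×√0.1275)/0.15]² = 97.98, so 98.
- Allowance for drop-out: 98 × 1.1 = 107.8, so 108 per arm and 2 × 108 = 216 active subjects.

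The z-tests carry no covariates, so none of this changes.

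**2. Dose per kilogram (arithmetic on the documents' doses).**

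| Weight | 8 mg | 16 mg |
|---|---|---|
| 40 kg | 0.20 mg/kg | 0.40 mg/kg |
| 80 kg | 0.10 mg/kg | 0.20 mg/kg |
| 120 kg | 0.067 mg/kg | 0.133 mg/kg |

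Per kilogram, 8 mg at 40 kg equals 16 mg at 80 kg. All three weights are eligible. This shows what entry allows; it does not show that exposure scales with mg/kg.

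**3. Sex ratio produced by weight alone.** Suppose exposure is proportional to dose × weight^(−b), with no true sex effect. Then the female/male ratio is (W_men / W_women)^b. The documents give neither the weights nor b, so both are assumed.

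| b | 85 vs 72 kg | 85 vs 70 kg | Range, 85 vs 75 to 88 vs 68 kg |
|---|---|---|---|
| 0 | 1.00 | 1.00 | 1.00 |
| 0.25 | 1.04 | 1.05 | 1.03-1.07 |
| 0.5 | 1.09 | 1.10 | 1.07-1.14 |
| 0.75 | 1.13 | 1.16 | 1.10-1.21 |
| 1 | 1.18 | 1.21 | 1.13-1.29 |

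**4. What adding weight does.** A linear model of log AUC was simulated (216 active subjects, 2,000 runs, 20-30% women, exposure CV 30-50%, no true sex effect).
- *Bias.* Without weight, the sex coefficient is about 0.097 at b = 0.5 (e^0.097 = 1.10) and about 0.19 at b = 1 (e^0.19 = 1.21). With log weight in the model it returns to about 0.
- *Precision of sex.* At b = 0 the standard error rises by 10-13% (for example 0.050 to 0.055, and 0.071 to 0.080). At b = 0.75 the change runs from none to 10% larger. It falls, by about 10%, only at b = 1 with CV 30%.
- *Precision of the dose contrast.* The standard error is unchanged at b = 0, 2-5% smaller at 0.5, 3-10% smaller at 0.75 and 6-18% smaller at 1.

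**5. BMI is not a stand-in for weight.** BMI 24.9 at 1.90 m is 24.9 × 3.61 = 90 kg; BMI 30 at 1.50 m is 30 × 2.25 = 67.5 kg. The heavier subject falls in the lowest BMI class and the lighter one in the highest.

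**The case against.** Much can be said for leaving the plan alone, and several parts of the case stand.

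- **Body size is not ignored.** A reader might infer that it is. In fact BMI classes are planned for the primary and the other PD endpoints, and SAP 5.4.1 repeats the demographic table by gender, so a weight imbalance would be visible. Neither step reaches PK or adjusts the sex contrast.
- **No PK sex test is planned.** A reader might infer a high rate of false sex findings. In the simulation, a nominal 5% sex test without weight rejects in 22-60% of trials at b = 0.5 and 44-91% at b = 0.75. But SAP 6.9 contains no such test, and at b = 0 the rate is the nominal 5%. The unadjusted female/male ratio under fixed dosing is also a legitimate description. What fails is reading it as an effect of sex itself.
- **The size is assumed.** Weight cannot be called the main source of exposure variation from these documents. Redacted text may bear on it.
- **The PD effect may be small.** Protocol 1.3.2.3 reports peak inhibition above 85% from 4 mg, and a mean of at least 85% for about 6 h at 16 mg. A modest exposure shift need not change response through 4 h.
- **Interaction terms are costly in the logistic model.** Log weight with treatment × log weight adds three parameters. At the targeted 85% response, each active arm has about 0.15 × 108 = 16 non-responders. This is a good reason to keep these terms out of the main PD models.
- **The phase 3 modelling could include weight.** Its covariates are not described, so an omission there is not shown.

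**Conclusion.** The point holds as a gap in the exploratory analyses. The objective on other covariates has no body-size analysis for PK, and sex is reported or modelled throughout without weight. Over the assumed weights and exponents 0 to 1, weight alone would produce a female/male exposure ratio between 1.00 and 1.29, or about 1.09-1.10 at exponent 0.5 with 85 versus 70-72 kg. No corresponding figure for PD response was derived. For PD the distortion would be diluted, because weight can act through the drug only in the active arms while the sex term spans all three arms.

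A reader might go further and conclude that the trial loses precision on its main comparisons, or that they are biased. The documents do not support that. The deciding z-tests have no covariates, randomisation protects the dose-placebo contrasts, the gain for a modelled dose contrast is mostly below 10%, and the sex coefficient usually becomes less precise once weight is added. The case rests on less confounding of the sex contrast. It is a cheap improvement worth making and poses no threat to the primary result.

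**What to change.** - **SAP 6.9.** Add an exploratory linear model of log Cmax and log AUC0-24h on dose, injection site, sex, age and log body weight. Add a PK summary by weight or BMI class. Report the sex ratio with and without weight side by side.
- **SAP 6.8.1.2 and 6.8.2.2.** Add log weight, with treatment × log weight where the data allow, to the logistic, longitudinal and 8 h status models as a sensitivity analysis only. A main effect alone would not capture an effect that arises only through the drug.
- **SAP 11.4.** Record these as additional analyses, since that section now lists none.

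The z-tests, sample size and dosing stay as they are. Weight is already collected, so the cost is SAP wording, some programming, a few degrees of freedom, and usually a slightly wider interval for the sex coefficient (about 10-13% if weight has little effect).

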5.1.2 Study treatment supply

Manufacture, labeling, packaging, and supply of study treatment will be conducted according to Good Manufacturing Practice, Good Clinical Practice (GCP), and any local or national regulatory requirements.

All study treatment supplies are to be used only in accordance with this protocol, and not for any other purpose.

5.1.2.1 Study treatment packaging and labeling

Study treatment (ACT-246475 and matching placebo) will be provided in sealed glass vials as a lyophilizate to be reconstituted by a pharmacist or an authorized person as per local regulation.

Study treatment will be labeled to comply with the applicable laws and regulations of the countries in which the study sites are located.

5.1.2.2 Study treatment distribution and storage

The investigator is responsible for safe and proper handling and storage of the study treatment at the investigational site and for ensuring that the study treatment is administered only to subjects enrolled in the study and in accordance with the protocol.

5.1.2.2.1 Study treatment distribution

The study centers will be supplied with study treatment according to the centers' needs, depending on the rate of subject enrollment. Each center will have an individual stock of study treatment, which will be re-supplied continuously as soon as a predefined minimum number of study treatments have been reached.

5.1.2.2.2 Study treatment storage

Study treatment must be kept in a locked room or a locked cupboard in a restricted access room, which can be accessed only by the pharmacist, the investigator, or another duly designated person as specified on the delegation of authority form.

A temperature log must be maintained and temperature check will have to occur at least on a weekly basis at the site. The sponsor/delegate will provide a temperature log; however, the use of the log is not mandatory if the site has an acceptable means of recording the temperature. Any temperature recording system routinely used at the site will be acceptable as long as all required information is included and certification of calibration is provided. If the temperature is captured electronically, a print-out will be made available to the CRA during each on-site visit.

If a deviation from the approved temperature range is identified by the study center, the deviation must be reported to the CRA, preferably in writing and with supporting documentation (e.g., copy of the temperature log showing data for all excursion days). The CRA will immediately contact the sponsor for further advice. The affected study treatment must not be used (e.g., it will be segregated physically at the study center) until confirmation from the sponsor is obtained that its use is safe. If the temperature deviation is outside of the acceptable limit, the study treatment will be kept segregated at the study center and returned to the sponsor following internal study treatment return processes. New study treatment supplies will be provided to the study center.

Temperature deviations correspondence must be kept in the Investigator Site File (ISF).

5.1.2.3 Study treatment return and destruction

On an ongoing basis and/or on termination of the study, the CRA will collect used and unused treatment kits, which will be returned to the warehouse. In certain circumstances, used and unused study treatment containers may be destroyed at the site once study treatment accountability is finalized, has been verified and reconciled by sponsor personnel or the deputy, and written permission for destruction has been obtained from the sponsor. Further details are provided in the study treatment handling manual.

5.1.3 Study treatment assignment and dispensing

5.1.3.1 Study treatment assignment

At Visit 2, after having verified that the subject meets all inclusion criteria and none of the exclusion criteria, and after performing the pre-dose VerifyNow® assessments, the platelet aggregation technician will provide the PRU stratification group to the person who will randomize the subject using the Interactive Response Technology (IRT) system. The IRT will assign a randomization number to the subject and will assign the treatment kit number as well as the dose and injection site, which matches the treatment arm assigned by the randomization list to the randomization number.

The randomization list will be generated by an independent Contract Research Organization (CRO).

5.1.3.2 Study treatment dispensing

The IRT will allocate one treatment kit (1 vial) per subject at randomization. In the event of deviation from study treatment preparation instructions [Section 5.1.4] (e.g., breach of sterility conditions, incorrect dose), a new kit will be requested via the dispensing module of the IRT and preparation steps will be started again. The protocol-mandated study treatment dispensing procedures may not be altered without prior written approval from the sponsor. An accurate record of the date and amount of study treatment dispensed to each subject must be available for inspection at any time.

5.1.4 Study treatment preparation and administration

Detailed information about the study treatment preparation and stability of the solutions is provided within the study treatment handling manual.

The preparation of the study treatment must be done under aseptic conditions by a pharmacist or an authorized person according to local regulation.

The sealed glass vials containing the study treatment will be reconstituted with 1 mL of water for injection. The resulting stock solutions will be at a concentration of 20 mg/mL ACT-246475. For subjects randomized to receive the 8 mg dose of ACT-246475 or its matching placebo, dilution of the stock solution will be performed with 1 mL of NaCl 0.9% to obtain the required concentration for injection [Table 1]. For all doses, the total volume administered will be 0.8 mL (i.e., concentration of the solutions adapted).

The reconstituted ACT-246475 solution will be injected as s.c. single dose in the anterior mid-thigh skin or abdomen skin through [REDACTED] needle. The injected volume will be 0.8 mL for all subjects [REDACTED].

The protocol-mandated study treatment administration procedures may not be altered without prior written approval from the sponsor. An accurate record of the date and amount of study treatment administered to each subject must be available for inspection at any time.

In [Table 1](#), the preparation of doses of the study treatment is described; detailed instructions are given in the study treatment handling manual.

The date and start time of preparation of the injection solution as well as the procedure must be recorded on source documents.

Table 1 Preparation of study treatment for subcutaneous administration

Study treatment	Dose	Volume of water for injection	Volume of NaCl 0.9%	Stock solution concentration	Aliquot of stock solution to be administered
ACT-246475 or placebo	8 mg	1 mL	1 mL	10 mg/mL	0.8 mL
ACT-246475 or placebo	16 mg	1 mL	-	20 mg/mL	0.8 mL

5.1.5 Blinding

This study will be performed in a double-blind fashion. The investigator, study personnel, subjects, sponsor personnel, and CRO personnel involved in the conduct of the study will remain blinded to the study treatment (ACT-246475 or placebo).

The dose (8 mg or 16 mg) will be blinded only for the subject. The injection site (thigh or abdomen) will not be blinded.

Sponsor staff responsible for clinical trial supply distribution will be partially unblinded at depot level to ensure adequate study oversight, but will remain blinded to subject randomization and subject treatment.

Sponsor staff responsible for suspected unexpected serious adverse reaction (SUSAR) management may be unblinded to some subject treatment allocations. These persons will be clearly identified, their unblinding will be documented in the TMF and they will not take part in any Clinical Trial Team (CTT) meetings after study set-up has been completed.

The CRAs and the site technician performing the platelet aggregation assays will have access to the platelet aggregation test results (VerifyNow® and LTA) and will, therefore, be considered unblinded (they will not have access to the randomization list).

The randomization list will be kept strictly confidential and accessible only to authorized persons, sponsor quality assurance (QA), and the PK analytical laboratory who are not involved in the conduct of the study, as long as the blinding needs to be maintained until final data analysis.

The investigational treatment and its matching placebo are indistinguishable, and all treatment kits will be packaged in the same way.

